### **3.0 Intervention to be studied**

Early mobilization is a widely accepted pillar of acute hospital therapy services. In most populations, early mobility is regarded as safe, feasible, and yields positive results. A considerable amount of clinical and scientific literature has evaluated and upheld the positive effect of early mobility on patient safety, ICU delirium, duration of mechanical ventilation, hospital length of stay, functional mobility, ambulation ability, and mortality. However, most of the research in the field of early mobilization has focused on intensive care patients with multiple medical comorbidities.

The consideration of an acute stroke diagnosis in relation to the approach of acute care PT and “early mobility” is limited. The AVERT trial was novel in opening the doors to considering physical therapy’s approach to acute stroke care on these dedicated stroke units, critical since earlier research surmised that complications of immobility could be estimated to account for as many as 51% of death in the first 30 days post stroke. The results of the AVERT trial, however, raised concern that very early mobilization may cause changes in cerebral blood flow and blood pressure leading to worsened stroke outcomes, increased mortality and increased rate of falls during early mobility.

From the publication of the AVERT trial, there has been a rise in clinical interest regarding the correlation of early mobility and improved functional outcomes post stroke. The majority of physical therapy studies in the acute stroke population have only examined the optimal time to begin mobilization post admission to the hospital. This project proposes the idea that patients with acute stroke may not be able to tolerate an extensive early mobility program.

Instead, patients may benefit from shorter more frequent sessions of therapy early in their recovery to focus on specific areas such as seated postural control, motor recruitment strategies, and transfer training delivered in separate sessions. We hypothesize that the approach of shorter, more frequent sessions of intense quality therapy services will negate the post stroke fatigue factor. Thus, allowing patients to progress functional mobility with improved tolerance to therapy sessions, frequent repetition, as well as implementation of motor learning principles to ensure carryover by providing distributed over massed practice.

The research in the field of neuroplasticity and neuro rehabilitation illustrates the importance of high intensity, repetitive and aggressive approaches for motor recovery, however, most of this research has been performed in the subacute stroke population. Error augmentation training is one way to increase the difficulty of a task to enhance motor learning. In the current research, Error amplification training was found to induced more robust aftereffects after locomotion training as compared to assistive training. Thus, error augmentation/amplification may be one approach to increasing the intensity and complexity of the task without changing the task itself. For acute stroke patients in the hospital setting- error augmentation can be implemented by targeting the patients post stroke deficits by emphasizing them. If a patient has a hemiparetic limb- error augmentation would include resisting and challenging the movement of that limb rather than facilitating and assisting with the movement of that limb. For patients whose stroke did not cause hemiparesis but rather balance impairments, narrowing the base of support or dynamically resisting balance in the direction of a patient's lateral lean can also amplify and augment their error. The celebrated motor learning theory, "The Challenge Point Theory" states that learning is maximized when the task difficulty is appropriate for the individual skill level of the performer; this theory leaves us with hope that increasing the challenge of mobility tasks in the acute hospital setting may be beneficial to increasing the success and progress of functional mobility.

Rather than decreasing the time to upright mobility, it may be beneficial to examine the effect of short sessions of more frequent challenging mobilization in these patients, within the early stages of their hospitalization. If, as assumed, a prolonged duration of upright sitting posture has a negative effect on cerebral blood flow it may be possible to gain the positive effects of early mobility by continuing to provide PT services while combating the negative effects of cerebral perfusion by returning all patients to a supine position in bed following therapy services within the first 24 hours of acute stroke. This study aims to examine the approach of increased frequency and intensity of physical therapy services as a way to gain the benefits of the publicized early mobility approach, while weighing the concerns raised by previous trials and decreasing amount of time left upright to combat negative effects of cerebral perfusion on the ischemic penumbra. As part of this study, there will be an experimental group of participants who will receive PT sessions twice a day for the first three out of five days of admission, followed by daily treatment sessions at an intensity of at least 20-50-minute sessions. The intensity of the treatment provided to the

treatment group will be increased by incorporating error augmentation training. Error augmentation/amplification is an approach to increasing the intensity and complexity of the task without changing the task itself- thus, allowing the treatment group to participate in the same protocol of bed mobility, transfers and gait training as the control group- except with amplification of their errors rather than correction of these errors. This group will be compared to a group of control participants who will receive standard PT services 3-5x/wk (on average 20-50 minutes/session) while in the acute hospital setting.

Outcomes of interest include average length of stay, discharge disposition, Postural Assessment Stroke Scale & Modified Rankin Scale scores, and rate of readmission at 30 days. There is a critical need to evaluate how the mobilization approach of patients with acute stroke during their hospitalization impacts their discharge disposition, length of stay, and future functional outcomes

#### **4.0 Study Endpoints**

Physical Performance and Functional Measures: PASS scores & AMPAC scores on evaluation, day three, discharge, and 90 day follow up. Discharge disposition recommended vs ultimate discharge disposition, hospital length of stay, and 30-day readmission.

#### **5.0 Inclusion Criteria**

Inclusion/exclusion criteria will be determined based on patient chart review in EPIC, once PT consults are received. Thorough chart review and discussion with patient's medical team will serve as a means of determining patient eligibility. Both treatments as usual and experimental group patients will meet the same eligibility criteria and will be randomized to their treatment after consent is obtained.

##### **Inclusion Criteria:**

Acute stroke

NIH Stroke Scale score of 2-18 with motor involvement

Age </=80yo

Medical stability for increased therapy services, determined by Stroke Service NP

Ability to give informed consent

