## **10.0 Study Design:**

This study will be designed as a randomized control trial with a 1:1 randomization. This study will utilize a permuted block design to randomly allocate a participant to a treatment group, while maintaining a balance across treatment groups. All patients will be identified and consented within 24 hours of admission.

The treatment group will receive increased frequency of PT services within the first 3-5 days of admission, followed by daily PT services for the duration of their inpatient stay. As part of the increased intensity of the treatment provided- this group will receive error augmentation training where the treating therapist will induce errors throughout mobility to challenge the patients rather than facilitating error-free movement. The deficits identified on evaluation will be targeted and emphasized throughout all therapy sessions. For patients with hemiparesis, the hemiparetic limb will be resisted during mobility. For patients with balance impairments- balance will be challenged by narrowing the base of support and resisting midline positioning

toward the side of the balance impairment. The treatment as usual group will receive standard care of PT services 3-5 times per week during their hospitalization which focuses on performing bed mobility, transfers and ambulation vs wheelchair mobility as able. Safety will be ensured throughout therapy sessions. Fall risk will be avoided with the use of a gait belt and non-skid socks and cerebral perfusion concerns will be mitigated by checking a resting blood pressure prior to upright mobility. The Postural Assessment Stroke Scale will be obtained as part of the initial PT clinical evaluation, on day three of hospital admission and at 90 day follow up. Follow up will be conducted (at 90 days +/- 15 days) via neurology clinic- either in person, through virtual clinic or, patient will be contacted via password protected Zoom. NIHSS and MRS scores will also be obtained from patient's chart on admission and at 90 day follow up. All of this data will be collected prospectively for both groups for this research study.

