Precaution will be taken to lessen the probability of risks; despite increased frequency of treatments, duration of upright will still be approached cautiously within the first 24 hours s/p stroke for cerebral perfusion. ALL stroke patients will be returned to supine within 24 hours post stroke and maintain head of bed <30 degrees except for medication, meals, and therapy. Therapy will be stopped if patient deemed medically unstable for increased frequency of treatments by the Stroke NP, Attendings, Fellow, or PI; this decision will be documented via "bed rest" orders in the patient's electronic medical chart, so that the study team is aware to avoid progressive frequent upright mobilization.

**Data collection:** Patient data will be collected from their medical record. Data collected from EPIC/patient's MUSC EMR will be coded in the research database. Data collected include:

- 1) Demographics: sex, age, race
- 2) Stroke risk factors: history of HTN, HLD, A-fib, or DM
- 3) Stroke specifics: type of stroke (hemorrhagic vs ischemic), location of stroke, stroke severity (measured by NIHSS & MRS), time of symptoms to presentation, intervention (tPA or thrombectomy) and complications
- 3) Physical Performance and Functional Measures: Postural assessment stroke scale scores on evaluation, day three and 90 day follow up. Discharge disposition recommended vs ultimate discharge disposition, hospital length of stay.

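### Eligibility spans NIHSS 2 to 18, yet severity is neither a stratification factor in the randomisation nor a covariate in the models, although admission NIHSS is already collected

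*Combined protocol and SAP*

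**What the plan says.** **Severity range.** The Inclusion Criteria in Section 5.0 require "NIH Stroke Scale score of 2-18 with motor involvement". They give no assessment time for the score and do not define the motor clause. The same section settles eligibility from the chart: "Inclusion/exclusion criteria will be determined based on patient chart review in EPIC, once PT consults are received".

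**Allocation.** Section 10.0 specifies a 1:1 permuted-block design. It names no stratification factor. Enrolment has a one-day window: "All patients will be identified and consented within 24 hours of admission".

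**Data available.** Section 10.0 states that "NIHSS and MRS scores will also be obtained from patient's chart on admission and at 90 day follow up". Its data-collection list also records NIHSS and mRS as the severity measures, together with "time of symptoms to presentation, intervention (tPA or thrombectomy) and complications".

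**Analysis.** Section 11.0 plans mixed models for all outcomes and logistic mixed models for outcomes split into favourable and unfavourable. It discusses the covariance structure, multiplicity and missing data. It lists no baseline covariate.

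**Patients the intervention describes.** Section 3.0 gives one technique for a hemiparetic limb and another "For patients whose stroke did not cause hemiparesis but rather balance impairments". Section 10.0 repeats both techniques. Its balance sentence does not say that hemiparesis is absent. It adds that "The deficits identified on evaluation will be targeted and emphasized throughout all therapy sessions".

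**The concern.** A trial that enrols from NIHSS 2 to 18 mixes mild strokes with fairly severe ones. Severity at entry can be expected to predict where a patient goes on discharge and the 90-day mRS, whichever arm the patient is in. Permuted blocks without strata keep the arms equal in size. They do nothing to keep them equal in severity.

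Two things are at stake. With 75 per arm, a visible severity difference between arms is fairly likely. A reader of the disposition or mRS result would then ask whether it reflects therapy or case mix, and the plan has no prespecified adjusted analysis with which to answer. Severity adjustment chosen after seeing the baseline table is less persuasive than adjustment written down beforehand. Second, leaving out a strong baseline predictor leaves avoidable noise in the comparison even when the arms happen to be balanced.

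The eligibility wording is a smaller matter. Two staff members, one using the admission score and one using the latest score in the chart, could reach different decisions on the same patient while both follow Section 5.0.

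**Working it through.** **The plan's own figures.** The plan gives no figure for severity balance. Its precision figure for PASS, a 95% margin of error of 2.3 with 75 per arm (Sections 6.0 and 11.0), is reproduced with SD 7.20:

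1.96 × 7.20 × √(2/75) = 2.30.

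With SD 7 the result is 2.24. This point does not dispute that figure.

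**Inputs for the imbalance check**
- n = 75 per arm: Sections 6.0 and 11.0.
- No stratification: Section 10.0 names no factor.
- Share p of patients in the more severe of two NIHSS bands: not in the documents. I assume 40% and show 20% to 50%.

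**Formulas.** The difference between arms in the proportion of severe patients has

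SE = √(2 × p × (1 − p) / 75).

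The chance of an absolute difference of 10 percentage points or more is 2 × [1 − Φ(0.10 / SE)], and the 95% range is ±1.96 × SE.

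**Result at p = 0.40**
- SE = √(2 × 0.4 × 0.6 / 75) = √0.0064 = 0.080.
- 0.10 / 0.080 = 1.25, so the chance is 2 × (1 − Φ(1.25)) = 0.21.
- 95% range: ±1.96 × 0.080 = ±15.7 percentage points.

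**Sensitivity to the assumed share**

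| Share p | SE | 0.10 / SE | Chance of ≥10 points | 95% range (points) |
|---|---|---|---|---|
| 20% | 0.065 | 1.53 | 13% | ±12.8 |
| 30% | 0.075 | 1.34 | 18% | ±14.7 |
| 40% | 0.080 | 1.25 | 21% | ±15.7 |
| 50% | 0.082 | 1.22 | 22% | ±16.0 |

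Ten points of 75 is 7.5 patients, so in whole patients the event is a difference of 8 or more. An exact calculation with two independent binomials at p = 0.40 also gives 21%.

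**What an imbalance does to an outcome.** If the two bands differ by D in an outcome, an imbalance of 0.10 moves the unadjusted between-arm difference by 0.10 × D in that one trial. The documents do not give D for disposition, mRS or PASS, so I put no figure on the shift.

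**The wording point, side by side**
- Section 5.0 requires motor involvement. Section 3.0 describes patients with impaired balance and no hemiparesis. If the clause means limb weakness, Section 5.0 refuses these patients. If it includes impaired postural control, the sections agree. Nothing in the documents chooses between the readings.
- The only scheduled NIHSS before treatment is the admission score in Section 10.0. It appears there as data collection and is not linked to eligibility. Consent may follow by up to 24 hours, and patients given tPA or thrombectomy are recorded and not excluded, so the admission score and a later score may differ.

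**The case against.** **Chance imbalance is not bias.** Correct. Randomisation is unbiased without strata, and the 5% test already allows for chance differences. This limits the point to precision and credibility, but it does not remove the gain from using a baseline value that is collected anyway.

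**The primary outcome is partly protected.** PASS is measured at the initial evaluation and analysed by a repeated-measures model, so baseline status on PASS itself is observed. This stands. The gain from NIHSS is probably smallest for PASS and larger for disposition and mRS, neither of which is primary.

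**The 40% share is invented.** It is an assumption and is labelled as one. Between 30% and 50% the answer changes little (18% to 22%); at 20% it falls to 13%.

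**Adjustment alone would do.** Largely true. A prespecified covariate recovers much of the benefit. Stratification adds balance that is visible in the baseline table.

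**Stronger readings that the documents do not support.** A reader might infer that the eligibility rule contradicts the intervention. It does so only if motor involvement means limb weakness, which no section says; hemiparesis is the first group described, and Section 10.0 never refers to patients with balance impairment alone. A reader might also infer that patients who have recovered by evaluation dilute the PASS effect. No section requires a minimum remaining deficit, so such enrolment is possible. But a PT consult, the investigator's judgement of appropriateness and consent taken by a physical therapist (Sections 5.0 and 8.0) all come first, and the documents do not say how many such patients would pass. No dilution figure can be claimed.

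**Conclusion.** The concern holds as a shortcoming in design and analysis. Severity is wide at entry, recorded at baseline, and used neither in the randomisation nor in the models. Assuming 40% of patients in the more severe band, an imbalance of 10 percentage points or more has about a 21% chance; over assumed shares of 20% to 50% the range is 13% to 22%. The consequence is lost precision and a result that is harder to defend, chiefly for disposition and mRS. The comparison is not biased, and the plan's PASS precision figure is not in question.

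The eligibility wording is an ambiguity to settle. Eligibility is decided before allocation and by the same criteria for both arms, so the ambiguity affects who is enrolled and how reproducible that is, not the fairness of the comparison.

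**What to change.** 1. **Section 10.0:** stratify the permuted blocks by pre-randomisation NIHSS in two bands, with the cut-point fixed in advance.
2. **Section 11.0:** prespecify NIHSS as a covariate in the models for PASS, AMPAC, mRS and disposition. For logistic models, state that the odds ratio is conditional on NIHSS, because adjustment changes what that ratio measures.
3. **Section 5.0:** state which NIHSS assessment decides eligibility, use the same score for stratification and as the covariate, and define motor involvement so that Section 5.0 agrees with Sections 3.0 and 10.0. Which patients should qualify is for the sponsor to decide.

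**Cost.** One extra randomisation list, and the chosen NIHSS must be on record before allocation. The last block in each band may be left incomplete, so arm sizes could differ slightly. If the admission score is chosen, no new measurement is needed. A later score would need one more data field. The documents name REDCap for data management only, so the allocation mechanism should be described at the same time. If stratification is no longer practicable, the prespecified covariate alone is still worth adding.

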##### **Exclusion Criteria:**

Medical instability or cerebral perfusion dependence, requiring bed rest

Pregnancy (noted in chart)

Inmates (noted in chart or visible by guards present at bedside)

Known & Current COVID-19 infection (PCR positive labs)

Dialysis (noted in chart & performed while inpatient)

External Carotid Stenting Procedure

#### **6.0 Number of Participants**

Goal enrollment is 150 participants. Based on the past literature, in similar populations the standard deviation of PASS measurements is at the most 7. Using this, with a sample of 75 patients in each group, with 95% confidence at the end of the study we can estimate this difference within a margin of error of 2.3.

#### **7.0 Setting**

This research will be conducted on the inpatient stroke service at MUSC (ED, 9E, 9W, 8W, ICU) within 24 hours of the patient's admission to the vascular neurology service for an acute stroke. Follow up values will be collected at post discharge neurology clinic (either in person or through password protected zoom call) by a member of the study team. Adverse events will be documented in the patient's medical chart and research record and the primary investigator will direct and oversee services provided. No additional safety risks are anticipated, other than those noted below (section 13.0)

## **8.0 Recruitment methods:**

Potential subjects will be identified via chart review on admissions to the stroke service and appropriateness of enrollment will be decided by PI based on discussion with the patient's clinical care team. Consent will be obtained by PT on initial evaluation. The PI/study team will already be part of these patients' clinical care and the PT or nurse practitioner obtaining consent will be an approved member of the study team on the eIRB application.

This study will also recruit from the Registry for Stroke Recovery (RESTORE-Pro#00037803, IRB approved 9/6/14) which is a research tool sponsored by the National Institutes of Health (NIH) Center of Biomedical Research Excellence (COBRE) in Stroke Recovery with subjects consented for future contact to support stroke recovery research conducted at MUSC. RESTORE staff will query the registry for potential subjects and provide the Principal Investigator (PI) with the contact information of subjects who meet their criteria. The PI or research staff will contact subjects to further screen for potential enrollment.

## **9.0 Consent process:**

To conduct this research, we will require a signed informed consent from all patients. The signed informed consent is necessary to be randomized to either arm of the study. A written copy of the consent form will be provided to the patient in the hospital prior to PT evaluation. The participant will be given the opportunity to read the consent, their questions will be answered and they will be provided with a copy of the consent document. Capacity to consent will be determined by the patient's primary medical team. For patients who are unable to physically sign their name, they may use make a mark on the consent and there will be a witness to the consent process.

## **10.0 Study Design:**

This study will be designed as a randomized control trial with a 1:1 randomization. This study will utilize a permuted block design to randomly allocate a participant to a treatment group, while maintaining a balance across treatment groups. All patients will be identified and consented within 24 hours of admission.

The treatment group will receive increased frequency of PT services within the first 3-5 days of admission, followed by daily PT services for the duration of their inpatient stay. As part of the increased intensity of the treatment provided- this group will receive error augmentation training where the treating therapist will induce errors throughout mobility to challenge the patients rather than facilitating error-free movement. The deficits identified on evaluation will be targeted and emphasized throughout all therapy sessions. For patients with hemiparesis, the hemiparetic limb will be resisted during mobility. For patients with balance impairments- balance will be challenged by narrowing the base of support and resisting midline positioning

toward the side of the balance impairment. The treatment as usual group will receive standard care of PT services 3-5 times per week during their hospitalization which focuses on performing bed mobility, transfers and ambulation vs wheelchair mobility as able. Safety will be ensured throughout therapy sessions. Fall risk will be avoided with the use of a gait belt and non-skid socks and cerebral perfusion concerns will be mitigated by checking a resting blood pressure prior to upright mobility. The Postural Assessment Stroke Scale will be obtained as part of the initial PT clinical evaluation, on day three of hospital admission and at 90 day follow up. Follow up will be conducted (at 90 days +/- 15 days) via neurology clinic- either in person, through virtual clinic or, patient will be contacted via password protected Zoom. NIHSS and MRS scores will also be obtained from patient's chart on admission and at 90 day follow up. All of this data will be collected prospectively for both groups for this research study.

Precaution will be taken to lessen the probability of risks; despite increased frequency of treatments, duration of upright will still be approached cautiously within the first 24 hours s/p stroke for cerebral perfusion. ALL stroke patients will be returned to supine within 24 hours post stroke and maintain head of bed <30 degrees except for medication, meals, and therapy. Therapy will be stopped if patient deemed medically unstable for increased frequency of treatments by the Stroke NP, Attendings, Fellow, or PI; this decision will be documented via "bed rest" orders in the patient's electronic medical chart, so that the study team is aware to avoid progressive frequent upright mobilization.

**Data collection:** Patient data will be collected from their medical record. Data collected from EPIC/patient's MUSC EMR will be coded in the research database. Data collected include:

- 1) Demographics: sex, age, race
- 2) Stroke risk factors: history of HTN, HLD, A-fib, or DM
- 3) Stroke specifics: type of stroke (hemorrhagic vs ischemic), location of stroke, stroke severity (measured by NIHSS & MRS), time of symptoms to presentation, intervention (tPA or thrombectomy) and complications
- 3) Physical Performance and Functional Measures: Postural assessment stroke scale scores on evaluation, day three and 90 day follow up. Discharge disposition recommended vs ultimate discharge disposition, hospital length of stay.

